11. METHODOLOGY

The registry is designed to document the disease progression in patients with advanced renal cell carcinoma, relapsed/refractory mantle cell lymphoma, and gastrointestinal stromal tumor intended by the treating physician for systemic therapy.

During the course of the registry, the following (minimum) number of survey times and endpoints are planned:

At observation start: Enrollment Visit

During the course of the observation: Follow-up documentation (as per local guidelines, generally every

8 - 12 weeks)

End of observation: Completion/Discontinuation Form

1-year follow-up for subjects who discontinue therapy: Survival form (every 6 months thereafter)

[figure not shown]
The temporal sequence and number of follow-up documentation items depends on medical practice to perform confirmatory imaging procedures and patient survival.

The completion of the continuous observation documentation (follow-up visits) takes place with the completion or discontinuation of the case report form below:

- Patient death.
- Patient lost to follow up due to patient request/withdrawal of patient informed consent,
- Change in therapy or discontinuation due to intolerance to temsirolimus, sunitinib, and axitinib or progression.

For the indication **metastatic renal cell carcinoma**, prospective documentation of sequential therapy is an option. According to the approvals of temsirolimus, sunitinib and axitinib, e.g. the following therapy sequences are possible:

• Sunitinib (as first-line therapy) followed by axitinib

- Temsirolimus (as first-line therapy) followed by sunitinib
- Axitinib (as second-line therapy, 1st Pfizer therapy sequence) followed by sunitinib
- Sunitinib (as first-line therapy) followed by a second-line approved active substance (interim documentation) followed by axitinib (in the third line or a later line)

Herein two consecutive Pfizer lines of therapy or two Pfizer lines of therapy with one or more intermediate therapies can be documented. The following documentation sheets are available for this purpose:

White documentation section: 1. Pfizer Therapy sequenze, e.g. Sunitinib

- Enrollment Visit
- Follow-up documentation every 8-12 weeks
- Final Assessment/Discontinuation of documentation

Pink Documentation section. Interim documentation for non-Pfizer products, e.g. nivolumab

• Every 8-12 weeks

Green documentation section. 1. Pfizer Therapy Sequence

- Initial visit to change treatment
- Follow-up documentation every 8-12 weeks

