- Final Assessment/Discontinuation of documentation

Survival Sheets

After two documented Pfizer therapy sequences for advanced RCC, or if the treatment of advanced RCC, mantle cell lymphoma or gastrointestinal stromal tumor is terminated, the documentation changes to the "survival sheets".

The query will be initiated for the first time 12 months after the final visit, then every 6 months thereafter. For this purpose, a separate case report form will be provided to you by Winicker Norimed.

[figure not shown]
The patient interview in the indication area will be conducted during therapy with temsirolimus, sunitinib and axitinib at each visit.

For the indications mantle cell lymphoma and gastrointestinal stromal tumors, only

the documentation for temsirolimus and sunitinib should be used:

- Enrollment Visit
- Follow-up documentation (as per local guidelines, generally every 8-12 weeks)
- Final Assessment/Discontinuation of documentation
- 1-year follow-up for patients who discontinue therapy: Survival form (every 6 months thereafter)

Safety Criteria

In contrast to the usual procedure in clinical trials, patients will not be selected at the start of treatment (baseline) for this register. According to Amendment VI, this investigation may provide new information on the safety of sunitinib, temsirolimus, and axitinib following sunitinib and other therapeutic options.

It is intended to document any intolerances that the physician observes during the observation period related to the documented medicinal products. Additionally, adverse events (AEs) and serious adverse events (SAEs) will be collected, as defined below.

In addition, the physician's subjective assessment of tolerability of the therapy will be obtained at each visit.

Efficacy Criteria

The efficacy of treatment with temsirolimus, sunitinib and axitinib will be assessed during routine treatment evaluation and documented at each visit based on the following tools (examinations):

[figure not shown]
- Computed tomography (if available) and/or
- Magnetic resonance imaging (MRI) (if available)
- Ultrasound examination (if available)
- Chest X-ray (if available)

The following criteria will be used to assess efficacy:

- Survival time (OS)
- Progression-free time (PFS)
- Physician's assessment of therapy response (CR, PR, SD, PD)
- Physician's assessment of efficacy and tolerability of the therapy

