The following is a schematic of all parameters to be recorded as part of this registry (imaging examination results if available).

Flow chart for the registry course for GIST and MCL

	Enrollment visit	Follow-up visit (every 8-12 weeks)	Completion Exam/ Discontinuation	Survival sheet (12 months after completion/ discontinuation)
Demographic data	X	X	X	Х
Inclusion/exclusion criteria	X			
Patient Informed Consent	X			
Tumor history	X			
Karnofsky Performance	X	X		
Treatment/Medication				
Pretreatment	X			
Concomitant medication	X			
Tumortherapy	X	X		Х
Safety				
Concomitant diseases/physical	X			
Lab values	X	X		
Electrocardiogram	X	X		
Documentation of adverse events		X	X	
Efficacy				
Subjective prognostic assessment by	X			
CT/MRI scan	X	X		
Ultra sound	X	X		
Chest X-ray	X	X		
Assessment of response to therapy by		X		
Therapy assessment of efficacy and tolerability		X		
Physician's overall assessment of therapy response			X	

Flow chart of mRCC sequence documentation:

	1 0 1		Interim documentation for non-Pfizer products	2. P	fizer Therapy Seq	SurvivalSheets		
	Enrollment Visit	Follow-up visit every 8-12 weeks	Completion/ Discontinuation of Documentation	Interim documentation every 8-12 weeks	Initial visit to change treatment	Follow-up visit every 8-12 weeks	Completion/ Discontinuation of Documentation	Survival Sheet 12 months after discontinuation, then every 6 months
Demographic data	X	X	X		X	X	X	X
Inclusion/exclusion criteria	X							
Patient Informed Consent	X			(x)				
Tumorhistory	X				X			
Karnofsky Performance Status/Height/Weight	X	X			X	X		
Treatment/ Medication								
Pretreatment	X							
Concomitant medication	X				X			
Tumor therapy	X	X		X	X	X		X
Safety								
Concomitant disease(s)/physical exam	X				X			

Labvalues	X	X			X	X		
Blood pressure	X	X			X	X		
Electrocardiogram	X	X			X	X		
Echocardiogram	X	X			X	X		
Pa in a ssessment	X	X			X	X		
Documentation of adverse events		X	X	X	X	X	X	
Efficacy		•				•		
Subjective prognosis assessment by the physician	X				X			
CT/MRI scan	X	X				X		
Ultra sound	X	X				X		
Chest X-ray	X	X				X		
Tumor Assessment		X		Х		X		
Physician's assessment of efficacy and tolera bility of the therapy		X				X		
Global assessment of therapy response by the physician			X	х			X	

Patient Quality of Life Survey	X	X			X	X		
-----------------------------------	---	---	--	--	---	---	--	--

Biometric evaluation

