Adverse events	X	X	X	X	X	X	X	

Efficacy								
Risk prognosis	X				X			
CT / MRT	X	X				X		
Ultrasound	X	X				X		
Chest X-ray	X	X				X		
Tumor assessment		X		X		X		
Physician's assessment of efficacy and tolerability		x				X		
Physician's overall assessment of treatment response			X	Х			X	
PRO: quality of life	X	Х			X	X		

Study population

It is planned to recruit 100 patients per year and treatment over a total recruitment period of 156 months, resulting in approximately 1.600 patients in summary. Patients should only be included after physician's decision to treat the patients with either Torisel®, Sutent® or Inlyta®.

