9 LIST OF TABLES AND TABLE SHELLS

If not otherwise specified, tables will be repeated for each combination of treatment and indication.

Table No.	Title	Treatment/ Indication	Analysis set	Description
1	Demography and Baseline Characteristics			
1.1	Disposition of patients			
1.1-1.1	Number of patients screened and reason for Non-inclusion	All	All patients	Counts over all treatments and indications (total number of patients in Star-Tor, total number of patients by indication, total number of patients by indication and treatment, total number of patients by indication and treatment sequence.
1.1-1.2	Treatment sequences	mRCC	All patients	Frequency table for sequences
1.1-1.3	Age of patients screened	All	Safety	Sample statistics for patients included and patients not included
1.1-2	Number of centers and patients planned and realized	All	Safety	number centers planned:200; number patients planned: 100
1.1-3	Number of patients per center	All	Safety	include number of active centers (e.g. at least 1 subject included)
1.1-4	Reason for premature discontinuation	All	Safety	Frequency tables for major reasons and specifications
1.1-5.1	Study duration	All	Safety	First patient in / Last patient out
1.1-5.2	Study periods	All	Safety Sequence analysis	Duration of study periods (Treatment phase, survival follow-up, sequence 1, sequence 2)
1.1-6.1	Summary of patient disposition	All	Safety	Patients who - were included into the study - were included into the Safety set - were included into the Safety set documented under prior versions of protocol - were included into the EAS - were included into the EAS documented under prior versions of protocol - Reason for exclusion from analysis set (refers to most comprehensive analysis set)

Table No.	Title	Treatment/ Indication	Analysis set	Description
1.1-6.2	Number of patients by time window	All	Safety, EAS	.1 Number of patients by visit .2 Number of visits by time window (table may be omitted, if only very few documented visits were condensed into one time window)
1.2	Demography			
1.2-1	Demographic variables	All	Safety, EAS Sequence analysis	age, sex, body height
1.2-2	Time-varying demographic variables	All	Safety, EAS Sequence analysis	Weight, BMI by time window
1.3	Medical and oncological history			
CCI				
CCI				
1.3-1.3	Current manifestations	MCL	SAFETY, EAS	Frequency tables for locations of manifestations

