In case an event (either death or progression) was present and date of event was documented, the following definitions was used:

Overall Survival (OS, months) = $\frac{\text{date of death} - \text{date of baseline visit} +1}{365.25 *12}$

Progression Free Survival (PFS, months) = (minimum of (date of death, date of progression) – date of baseline visit + 1)/365.25 * 12.

In case information on dates were partly or completely missing or contradictory, the following was done:

• PFS:

- o the presence of a progression was confirmed, but no date was documented: if date of last intake of study medication was given, this date was used as date of progression, otherwise the date of the last visit with a documented "non-progression (e.g. SD)" was used as date of progression.
- o the presence of a progression was confirmed, but dates within a visit and on final documentation were contradictory, the prior date was used.
- o in case a death was documented within a survival follow-up/ within sequence 2 for subjects from sequence 1, but no progression was documented within regular study, the date of last visit + 1 day was used as date of progression.
- o in case no progression was documented, subject was censored with the latest available contact date / assessment date within study/within sequence.
- o in case these rules led to a missing duration or a negative duration, duration was set to "1 day".

• OS:

- o in case a death was documented, but date of death was unknown, the date of death was substituted with the latest available date for the patient (last visit, last contact date, date of assessment)
- o in case no death was documented, subject was censored with the latest available contact date / assessment date within study.
- o in case these rules led to a missing duration or a negative duration, duration was set to maximum of (PFS,"1 day").

Response to therapy (Recist criteria/ Cheson criteria)

Response to therapy according to the Recist/ Cheson criteria will be analyzed using the physician's assessment as documented in the CRF. As neither "size of lesion", "new lesions" or "increase in size" are defined as key fields, contradictory answers will not overvote physicians assessment.

"Best response" will be analyzed using the physician's assessment at final visit. If "Best response" is missing it will be determined from the best response documented during previous follow-up visits.

Treatment

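### PFS may be censored at a survival-sheet contact with no tumour assessment, while a later death is backdated as an event, so recorded PFS depends on survival after tumour follow-up has ended

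*SAP*

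**What the plan says.** SAP Appendix 1, A1.3 (Survival) gives these rules:

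- PFS, no progression: "in case no progression was documented, subject was censored with the latest available contact date / assessment date within study/within sequence".
- PFS, death recorded in survival follow-up (or in sequence 2, for the sequence 1 analysis): if the patient died "but no progression was documented within regular study, the date of last visit + 1 day was used as date of progression".
- OS, no death: "in case no death was documented, subject was censored with the latest available contact date / assessment date within study".

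On the phases of the study:

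- SAP A1.1 defines a survival phase after discontinuation, with its own numbered time windows.
- SAP section 9, Table 1.1-5.2, is described as "Duration of study periods (Treatment phase, survival follow-up, sequence 1, sequence 2", so survival follow-up counts as a study period.
- Protocol section 11 lets regular documentation end on "Change in therapy or discontinuation due to intolerance to temsirolimus, sunitinib, and axitinib or progression", so it can end without progression.
- On the survival sheets, Protocol section 11 says "The query will be initiated for the first time 12 months after the final visit, then every 6 months thereafter". The mRCC flow chart agrees: "Survival Sheet 12 months after discontinuation, then every 6 months". The running text of SAP 2.1 instead counts the 12 months from baseline.
- In the SAP 2.1 flow chart, the row "Tumor assessment" is marked at follow-up visits of both Pfizer sequences and in the non-Pfizer interim documentation, but not in the survival column. That column has demography and tumour treatment only. The protocol flow charts show the same for the survival sheet.

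**The concern.** A PFS time is only as long as the period in which progression could have been recorded. If the censoring date may be any contact, a patient who stopped for intolerance or a change of therapy and is reported alive on a survival sheet stays in the PFS risk set throughout a period in which the registry collects no tumour assessment. No event can occur for that patient in that time, so the late part of the Kaplan-Meier curve is held up.

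The companion rule treats the same patient in the opposite way if death follows: stopping itself becomes the event. Whether stopping counts as an event or as the start of a long event-free interval then depends on survival after tumour follow-up has ended. Kaplan-Meier estimation does not allow for that.

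PFS is an effectiveness endpoint for every indication. The SAP reports its median and the 25% and 75% times with confidence intervals (8.1.2, Table 2.3-1), and plans log-rank tests between subgroups such as line, age, LDH and histology (Table 2.3-2).

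**Working it through.** The plan gives no figure that depends on this rule, so there is nothing to reproduce. The check has three parts.

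**1. Do the words reach survival-sheet contacts?** The PFS bullet allows a contact date within study or within sequence. Survival follow-up is a study period in Table 1.1-5.2. The OS bullet shares the within-study wording and must include survival contacts there. The PFS death bullet uses a narrower term, regular study, to set survival follow-up apart; the censoring bullet does not use it. So within study can include survival sheets. The sequence qualifier may stop the date earlier, but the text does not say when each alternative applies. It gives no clear protection to patients who pass straight from the analysed therapy to survival sheets. MCL and GIST patients are the plainest case, since they have one sequence only.

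**2. One patient, two outcomes.** Suppose a patient stops at month 4 without progression.

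- Alive at sheets 12, 18 and 24 months after the final visit: PFS censored at 4 + 24 = 28 months. With one sheet only: 4 + 12 = 16 months.
- Dies in survival follow-up: PFS event at about 4 months + 1 day.
- Difference: 12 to 24 months, with identical tumour follow-up.
- If the first sheet came 12 months after baseline, as the SAP 2.1 text has it, the first unobserved gap would be 12 − 4 = 8 months.

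**3. Effect on the curve (simulation).** These assumptions are not trial data: exponential progression with median 6 months; 10-30% stop without progression; median survival after stopping 12-24 months; data cut-off uniform over 12-60 months; sheets at 12 months after stopping, then every 6. The 6 months is borrowed from the run-time assumption for third-line axitinib in the protocol's case number estimate, where it is not called a median. The true values follow directly: median 6.0; 75% progressed at 2 × 6 = 12.0 months; 24-month PFS 0.5^(24/6) = 0.0625, about 6%.

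| Rules applied | Median (months) | 75% progressed (months) | 24-month PFS |
|---|---|---|---|
| Truth | 6.0 | 12.0 | 6% |
| Both SAP rules, survival contacts counted | 4.6-5.7 | 9.6-11.9 | 6-14% |
| Only the living patients' date moved to last assessment | 4.5-5.6 | 9.0-11.3 | 3-5.5% |
| Both rules changed | about 6.0 | about 12.0 | about 6% |

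Row 2 against row 3 isolates the contact-date rule: within scenarios it adds about 0.2-2.0 months to the 75% time and lifts the tail. Row 3 against row 4 isolates the death rule, which pulls everything down.

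A second simulation used progression detected at 10-weekly visits, death following progression, and true medians of 6 or 10 months. Under the SAP rules, 24-month PFS was 9-24% (true 6%) and 22-37% (true 19%). Moving only the living patients' date gave 3-6% and 10-18%. Changing both gave about 7% and 20-21%. The SAP-rule median fell below the truth in some scenarios and above it in others. Among living patients with at least one survival sheet, 63-89% had truly progressed by their censoring date.

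**The case against.** The strongest reply is that the PFS bullet is not the OS bullet: it adds the words on sequence. Both flow charts place survival information in its own column outside the Pfizer sequences, and Table 1.1-5.2 lists survival follow-up beside sequences 1 and 2. A reading that keeps survival contacts out of PFS is therefore available. This stands as far as it goes. The rule is ambiguous rather than plainly wrong, and the sponsor may have meant the narrower reading. But the text does not say so, and two programmers could derive different PFS dates from it.

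It is also fair that not every stop ends tumour follow-up. An mRCC patient who starts another drug may enter interim documentation or a second Pfizer sequence, and both carry tumour assessments. A reader might infer that nobody looks for progression after any final visit; the flow charts do not support that. The point is confined to patients who go directly to survival sheets.

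A reader might also infer that the plan simply inflates PFS, including the median. That holds only if later deaths are treated as censored. The SAP counts them as events at last visit + 1 day. With that rule applied, the median and the 75% time fell below the truth in the first simulation, and only the tail rose.

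Finally, the protocol calls the evaluation purely descriptive, the SAP has no hypotheses or decision rules, and 24-month PFS is not a listed output. This limits the consequences, but the same dates feed the published curves, quartiles and log-rank tests. Differential bias between drugs or subgroups is possible but has not been shown.

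**Conclusion.** The concern holds in this form: the PFS censoring bullet can credit living patients with time in which no tumour assessment was recorded, and together with the death bullet it makes PFS depend on later survival. For an affected patient the difference is a year or more by the protocol's schedule. Under the first simulation's assumptions, the contact-date rule raises 24-month PFS from about 3-5.5% to 6-14% (true 6%). With both SAP rules in force, the median is 4.6-5.7 months against 6.0, and the 75% time 9.6-11.9 against 12.0.

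The direction of net bias is not fixed. It depends on how many patients stop without progression and how long they then live, and the documents give neither. The figures show what the rules can do and are not estimates for this registry. They also take stopping to be unrelated to imminent progression. The change should be made before the final analysis.

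**What to change.** Change the two PFS bullets together. Moving only the living patients' date would leave the median and the 75% time slightly further from the truth (rows 2 and 3 of the table).

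- **No documented progression, not known to have died:** censor PFS at the last documented tumour assessment or response other than PD within the analysed sequence. If there is none, use the SAP's existing duration of 1 day.
- **Death in survival follow-up without documented progression:** censor at that same last assessment, instead of counting an event at last visit + 1 day. The bullet also covers deaths in sequence 2 for the sequence 1 analysis, which need the same treatment.
- State where a sequence ends for PFS, and reconcile the start of the survival sheets between the SAP 2.1 text and the flow charts.
- Keep the last contact date for OS only.
- Report PFS under the current rules as a sensitivity analysis, with the number of patients whose date or status changes. This also shows the size of the affected group.

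The cost is two rewritten bullets, a changed PFS date and event variable, and one more set of PFS outputs; no new data are needed. PFS follow-up will be shorter, there will be fewer PFS events, and some results will differ from earlier interim analyses, which should be explained in the report.

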8.1.2 Analysis Of Survival Data

OS, PFS and treatment duration will be analyzed using Kaplan-Meier plots. Median, 25% and 75% survival times with confidence intervals for OS and PFS will be presented. For stratification according to physician's prognosis and for risk groups according to Motzer score/MIPI/Fletcher risk table, log-rank tests will be performed.

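### Setting a missing or negative PFS to 1 day (OS to the larger of PFS and 1 day) turns date errors in patients with a documented event into events on the baseline-visit date

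*SAP*

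**What the plan says.** All the rules are in SAP 11.1, Appendix 1, A1.3, under Survival.

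- PFS is the earlier of the death and progression dates, minus the baseline-visit date, plus one day. OS is the death date minus the baseline-visit date, plus one day.
- For a confirmed progression without a date: "if date of last intake of study medication was given, this date was used as date of progression". Failing that, "otherwise the date of the last visit with a documented" non-progression supplies the date.
- If the dates on a visit form and on the final documentation disagree, the earlier one is taken.
- Patients without a documented progression (PFS) or death (OS) are censored at their most recent contact or assessment. An undated death takes the latest date known for the patient.
- Last PFS bullet: "in case these rules led to a missing duration or a negative duration, duration was set to" one day. The last OS bullet has the same condition but assigns the larger of PFS and one day.

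SAP 8.1.2 makes the affected quantities planned output: "Median, 25% and 75% survival times with confidence intervals for OS and PFS will be presented". In the mRCC flow chart of Protocol section 11, the row "Tumor Assessment" is not marked at the enrolment visit, only from follow-up onwards. SAP section 7 says that values still missing after queries are in general not replaced. The OS and PFS rows of the summary table in SAP 8.2.3 have nothing under missing data. No count of patients reaching the one-day rule is described, and no sensitivity analysis.

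**The concern.** The rule assigns the shortest time when the true time is unknown or the recorded one is impossible. Because it alters the duration and is silent on status, a confirmed event stays an event.

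Other rules can feed it. Taking the earlier of death and progression, or the earlier of two conflicting progression dates, lets one wrong pre-baseline entry displace a valid later date, after which day 1 is imputed. A patient who progresses at the first assessment has no earlier non-progression visit to fall back on.

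At stake is an artificial step at the start of the Kaplan-Meier curves. It would pull down the PFS quantiles and, where a death is misdated before baseline, those of OS. It would also enter the planned log-rank comparisons.

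**Working it through.** There is no figure in the plan to reproduce, so the check has two parts.

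**1. The rules applied literally to test patients.** The baseline visit is set at 10 March 2015 (an invented date). Duration = date − baseline + 1; the fallback applies only if the result is missing or below zero.

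| Test patient | Raw duration | Analysed as |
|---|---|---|
| A. Undated first-assessment progression, last intake 20 May 2015 | 71 + 1 = 72 | PFS 72 days, event; fallback not used |
| B. As A, but no last intake and no non-progression visit | missing | PFS 1 day, **event** |
| C. No event, last contact entered as 1 Sept 2014 | −190 + 1 = −189 | PFS 1 day, censored |
| D. Death entered as 1 Sept 2014, no progression | −189 | PFS and OS 1 day, **events** |
| E. As D, with valid progression on 10 Sept 2015 (day 185) | earlier date gives −189 | PFS and OS 1 day, **events** |
| F. Progression on day 185, alive, OS censoring date before baseline | OS negative | OS max(185, 1) = 185 days, censored |
| G. Event dated the day before baseline | −1 + 1 = 0 | 0 days; neither missing nor negative, so not caught |

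B, D and E are the problem. A progression on day 185 of the visit form with 1 Sept 2014 on the final documentation behaves like E for PFS, because the earlier of the two conflicting dates is taken. C causes no drop in the curve, and F shows a valid PFS protecting OS.

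**2. Size for patients who are otherwise like the rest (pre-baseline dates).** Let a share f be day-1 events and the remainder exponential with median m. The 25% time is the point by which a quarter have had the event.

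- Kaplan-Meier median = m × log2(2(1 − f))
- 25% time = m × log2((1 − f)/0.75)

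The relative changes do not depend on m. For scale, m = 6 months, taken from the remark in the case number estimate of Protocol section 11 that a progression event or death occurs after about 6 months; using it as an exponential median is my assumption.

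| f (assumed) | Median, months | Change | 25% time, months | Change |
|---|---|---|---|---|
| 0 | 6.00 | – | 2.49 | – |
| 2% | 5.83 | −2.9% | 2.32 | −7.0% |
| 5% | 5.56 | −7.4% | 2.05 | −17.8% |
| 10% | 5.09 | −15.2% | 1.58 | −36.6% |

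The absolute shift is the same at each quantile, −m × log2(1 − f): at f = 5%, 6.00 − 5.56 = 0.44 and 2.49 − 2.05 = 0.44 months. It therefore weighs most on the earliest quantile. In a group of 92, the number of sunitinib-axitinib patients the protocol gives for mid-2017, five affected patients (5/92 = 5.4%) would bring a 6-month median to 5.52.

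**Undated first-assessment progressions (patient B)** are not like the rest, so the table does not apply to them. With visits suggested every 8 to 12 weeks, their times are understated by roughly that much: 56 × 12/365.25 = 1.8 to 84 × 12/365.25 = 2.8 months. Moving an event earlier shifts a Kaplan-Meier quantile only if its true time lay beyond that quantile. The median then hardly moves; the 25% time falls only where it is shorter than the true progression time. In the illustration it is 2.49 months, inside the 1.8 to 2.8 range.

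**The case against.** The best defence is that few patients should get this far. Plausibility checks and queries come first (Protocol section 8, SAP section 7). An undated progression goes to last intake before anything else, so patient B needs three gaps at once. The evaluation is descriptive, and SAP section 4 declares hypotheses and decision rules not applicable. All of that stands. It limits the likely size and means that no error rate or power is affected. It does not justify the value assigned to those who remain, nor the absence of a count.

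A reader might infer more than the documents support:

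- *Every missing or negative OS becomes 1 day.* It becomes the larger of PFS and 1 day, so OS mainly reaches day 1 through a death misdated before baseline.
- *Everyone caught by the rule counts as a failure.* Patients without a documented event are censored at day 1.
- *These are failures on the first day of treatment.* Time runs from the baseline visit, and Protocol 10.2 allows for patients already on drug at consent.
- *All undated early progressions are affected.* Only those without a usable last-intake date.
- *Axitinib and later lines suffer most, because the earlier progression date is entered by mistake.* This is plausible, but the documents give no figure for it, and Protocol section 11 leaves retrospectively documented information out of the analysis.

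**Conclusion.** The point holds for patients with a documented event. The SAP states a rule that gives some of them a wrong time, the earliest one possible, and in some cases does so although a valid later date is on file. This is not a matter of missing detail.

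The direction is downward for PFS, and for OS where a death is misdated before baseline. The effect is largest in relative terms on the 25% time, which is a planned output. The size rests on three assumptions: the share f, which the documents do not give; exponential PFS; and affected patients being otherwise like the rest. It also rests on reading the rule literally, as leaving event status unchanged. The plan should be changed because the correction is cheap and the number affected would otherwise stay unseen.

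**What to change.** Replace the last PFS and last OS bullets in SAP A1.3 as follows.

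1. Before taking the earlier of death and progression, or the earlier of conflicting dates, treat any event date before the baseline visit as undated and use any valid date that remains. This also settles patient G and returns the PFS of patient E to day 185.
2. For PFS, then apply the existing steps: last intake, then last non-progression visit. If neither gives a valid date, use the visit at which progression was first recorded. For patient B, with a first visit at 8 to 12 weeks, that is day 57 to 85.
3. For OS, apply the existing rule for undated deaths, restricted to valid dates. Do not use the survival-form date: those forms first come 12 months after the final visit and then every 6 months, so they could place a death far too late.
4. State which substituted date PFS uses when a misdated death is its only event.
5. If no valid post-baseline date exists, exclude the patient from that time-to-event analysis and list the patient. Simply excluding or censoring all affected patients would be worse, because it would drop true early progressors.
6. Report the number handled this way per drug, and keep the 1-day rule as a sensitivity analysis.

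The cost is a short rewrite of the two bullets, a little programming and one count per table. A few patients may leave the time-to-event analyses.
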